2. Follow up through End of Study: Enter data at SOC visits where each subsequent (post palbociclib treatment) MBC treatment regimen is prescribed and at end of study.
3. Breast cancer treatment: including surgery, radiation, systemic chemotherapy, hormone therapy, and/or targeted therapy, in both neoadjuvant/adjuvant and metastatic disease settings, prior to, during, and post palbociclib treatment; supportive care is also collected in the metastatic setting while on this study.
4. Physician MBC Treatment Selection Survey: Treating physicians will complete a treating physician MBC treatment selection survey that will capture the reason(s) for treatment choice at start of palbociclib therapy and at start of subsequent therapies.
5. Clinical assessments: overall clinical response as judged by treating physician, at intervals per standard of care schedule: imaging assessment, clinical progression, and clinical biomarkers.

CCI

7. CBC: Baseline and during palbociclib treatment, enter any CBC during the 1st 3 cycles, then enter Day 1 (or prior to start of a new cycle) CBC for the subsequent cycles as per standard of care.

8. AE/SAE reporting begins at the time of the patient's first dose of palbociclib or the time of the patient's informed consent if s/he is already exposed to palbociclib and up to 28 calendar days following the last administration of palbociclib.

Table 2: EORTC QLQ-C30 and Geriatric Assessments

Data Collection and Entry	Baseline	Through End of Treatment with Palbociclib
	► SOC Visit 1	
EORTC QLQ-C30 ¹	x ¹	x ¹
G8 Screening Tool ²	x ²	x ²
ADL: Activities of Daily Living ²	x ²	x ²

ADL = Activities of Daily Living; EORTC QLQ-C30 = European Organisation for the Research and Treatment of Cancer Quality of Life Questionnaire Core 30

1. EORTC QLQ-C30 will be collected at baseline (before starting palbociclib) then monthly for the first 3 months of treatment with palbociclib, then every three months until the end of treatment with palbociclib.

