7 HANDLING OF MISSING VALUES

Given the prospective observational multi-site study design, missing data may occur, even though effort will be made to ensure consistent and complete data are collected. All available patient data will be used for analysis.

Date Imputations

For initial diagnosis date, date of prior therapy, date of prior radiation, or date of prior surgery:

- If the date of initial diagnosis has nonmissing month and year but the day is missing, the 15th will be inserted as the day.
- If the date of initial diagnosis has nonmissing year but the month and the day are missing, June 30th will be inserted.

For all other dates:

- If the variable is a stop or end date and day of the month is missing, the last day of the month will be imputed. All other dates with missing day of the month will be assigned the first day of the month.
- If the variables is a stop or end date and day and month are missing, 31 December will be imputed. All other dates with missing day and month will be assigned to 1 January.

Dates missing the year will be treated as completely missing.

Questionnaire Imputations

Missing data patterns will be explored using multivariable regression cross sectional analysis conducted at baseline and selected 6-month time points with completion of instrument (EORTC QLQ-30, G8, or ADL) coded as '1' and non-completion of the same instrument coded as '0'.

Additional information on missingness (e.g. reasons for withdrawal) may be explored. Scores associated with the EORTC QLQ-C30, G8, and ADL are addressed in section 8.9 Analyses Quality of Life Endpoints and Appendix 1 Data Derivation Details.

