Real-world tumor response (complete response, partial response, stable disease, progressive disease) is determined by physician based on imaging, biopsies, biomarkers, and/or clinical judgment. Response as assessed by Response Evaluation Criteria in Solid Tumors (RECIST) criteria may not be available for all patients. rwTR will be derived as the best tumor response recorded from the palbociclib combination treatment start date until the first documentation of progressive disease. Only response assessments recorded on or before the start date of next subsequent line of treatment will be considered. The proportion of patients with a best response of complete response, partial response, stable disease, and progressive disease will be calculated and reported. Real-world response rate is defined as the proportion of patients with a best tumor response of complete response or partial response. Best tumor response, clinical benefit, and study end date are defined in Appendix 1 Data Derivation Details.

rwPFS will be estimated by LOT in the ABC/MBC setting. rwPFS is defined as time (months) from initiation of the palbociclib combination treatment to the earliest of clinician-documented progression or death due to any cause, whichever occurs first. Patients absent of the above events will be censored at the last date of response assessment without progressive disease.

OS will be estimated by LOT in the ABC/MBC setting. OS is defined as time (months) from initiation of the palbociclib combination treatment to date of death due to any cause. Patients do not have a documented death will be censored at last available visit date known to be alive.

Follow-up time will be calculated as time (months) from initiation of the palbociclib combination treatment to date of death or last available visit date. Median follow-up time and range (minimum, maximum) will be provided overall and by LOT.

Time-to-event outcomes (i.e., rwPFS, OS) will be analyzed using the Kaplan-Meier method and estimated survival curves will be displayed when appropriate. The number of patients at risk over time will be presented. A summary table will include number of patients with events, number of patients censored, and Kaplan-Meier quartiles (when estimable) accompanied by two-sided 95% confidence intervals (CIs). Based on the Kaplan-Meier life table, Survival function estimates at the specific time points (eg, 6, 12, 18, 24, 30 and 36 months) will also be reported along with two-sided 95% CIs.

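### Partial death and progression dates go to the earliest possible day with no lower bound, so an imputed event can precede a known-alive visit, a dated progression or first dose

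*SAP*

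**What the plan says.** SAP section 7 (Date Imputations) sets up two groups.

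- **Initial diagnosis and prior therapy, radiation or surgery.** These get a mid-period value: with the day missing, "the 15th will be inserted as the day"; with day and month missing, 30 June.
- **All other dates.** The group is split. For the first part: "If the variable is a stop or end date and day of the month is missing, the last day of the month will be imputed", or 31 December if the month is missing too. For the rest: "All other dates with missing day of the month will be assigned the first day of the month" and "All other dates with missing day and month will be assigned to 1 January".

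The section closes with "Dates missing the year will be treated as completely missing".

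Death, progression and AE onset are not named in either group. No lower or upper bound on an imputed date appears in section 7, in section 8 (General Methods, Clinical Outcomes, 8.8.1) or in Appendix 1.

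These dates feed the time-to-event endpoints. SAP section 8 states: "OS is defined as time (months) from initiation of the palbociclib combination treatment to date of death due to any cause". rwPFS runs from the same start to progression or death, whichever is earlier. Patients without a documented death are "censored at last available visit date known to be alive"; that date is used for censoring only, not as a floor for a death date. General Methods computes any interval as the later date less the earlier one, plus one day, and converts to months by dividing by 30.4.

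For AEs, Protocol section 8.3 (Table 1, footnote 8) starts reporting at first dose, or at consent for patients already exposed, "and up to 28 calendar days following the last administration of palbociclib".

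**The concern.** A death or progression date is naturally read as neither a stop nor an end date, so a partial one moves to the earliest day it could have been. A patient seen alive on the 20th who dies later that month is recorded as dying on the 1st.

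Two other parts of the plan add to this. First, because rwPFS takes the earlier of progression and death, a death known only by year can override a fully dated progression in that year. Second, because the interval rule does not carry a sign, a death imputed before first dose does not show up as an error. It becomes a positive survival time that looks ordinary.

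At stake are individual OS and rwPFS times, the early part of the Kaplan-Meier curves, and the onset day of AEs around treatment start.

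**Working it through.** The plan gives no figure that depends on this rule, so there is none to reproduce. The rule was applied directly.

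**1. Mean shift.** Input: every calendar date from 2017 to 2021 (1,826 days), each taken as equally likely.

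- Day missing: shift = day of month − 1. In a 365-day year the sum is 7×(31×30/2) + 4×(30×29/2) + 28×27/2 = 3255 + 1740 + 378 = 5373, and 5373/365 = 14.7 days. Over the five years the mean is 14.73 days (14.73/30.4 = 0.48 months), maximum 30.
- Day and month missing: shift = day of year − 1, mean (365 − 1)/2 = 182 days. Over the five years it is 182.1 days (6.0 months), maximum 365.
- The SAP's own mid-period rule, on the same dates, is off by only about −0.7 and −1.9 days on average.

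**2. How often the imputed date precedes an anchor** (last visit or first dose) lying g days before the true event:

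| Missing | g = 7 | 14 | 21 | 28 | 30 | 90 | 180 |
|---|---|---|---|---|---|---|---|
| Day | 74% | 51% | 28% | 5% | 0% | 0% | 0% |
| Day and month | 98% | 96% | 94% | 92% | 92% | 75% | 50% |

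**3. Illustrative patients.** The SAP column is later − earlier + 1. The bounded column starts from the 15th or 30 June and applies a floor of the day after the last visit.

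| First dose | Last visit | Death recorded (true date) | SAP date | SAP days | True days | Bounded days |
|---|---|---|---|---|---|---|
| 20 Mar 2018 | 27 Mar 2018 | Mar 2018 (30 Mar) | 1 Mar 2018 | 20 | 11 | 9 |
| 15 Sep 2018 | 29 Oct 2018 | 2018 (10 Nov) | 1 Jan 2018 | 258 | 57 | 46 |
| 15 Sep 2018 | 29 Oct 2019 | 2019 (10 Nov) | 1 Jan 2019 | 109 | 422 | 411 |

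Row 2 in full: 15 September is day 258 of 2018, so the SAP gives 258 − 1 + 1 = 258 days (8.5 months). The truth is 314 − 258 + 1 = 57 days (1.9 months). The bounded date is 30 October: 303 − 258 + 1 = 46 days. Rows 1 and 2 lengthen survival; row 3 shortens it.

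**4. rwPFS override.** First dose 15 September 2018, progression dated 12 June 2019, death later in 2019 with only the year known. True rwPFS is 108 + 162 + 1 = 271 days (8.9 months). The SAP puts death on 1 January 2019, which is earlier than the progression, so rwPFS becomes 108 + 1 = 109 days (3.6 months).

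**5. Effect on a median.** The share of partial dates is not in the documents; 2–20% is assumed. The median of 24.8 months is borrowed from the PALOMA-2 figure in Protocol section 6.2. Event times are exponential, without censoring (simulation, 400,000 per scenario).

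| Share partial | Day missing | Day and month missing |
|---|---|---|
| 2% | 24.74 → 24.73 | 24.82 → 24.72 |
| 5% | 24.71 → 24.68 | 24.87 → 24.61 |
| 10% | 24.81 → 24.77 | 24.81 → 24.26 |
| 20% | 24.83 → 24.74 | 24.80 → 23.71 |

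As a rough check, share × mean shift at 20% gives 0.2 × 0.48 = 0.10 and 0.2 × 5.99 = 1.20 months, close to the simulated 0.09 and 1.09. Under these assumptions about 1.4% of day-missing and 15% of month-missing events fall before first dose. The simulation kept those as the earliest times. The unsigned rule would turn them into positive times of at most (365 + 1)/30.4 = 12.0 months, still below the median, so the median results are unaffected; the early curve is not.

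**6. AE onset.** Take an AE in the first-dose month, on or after first dose, with unknown day. With uniform start days and a constant AE rate, the chance that dosing began on the 1st, given such an AE, is 2/(L + 1) for month length L. With L = 30.4 this is 2/31.4 = 6.4%, so about 94% would be dated before first dose.

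**The case against.** **Death may count as an end date.** The SAP does not say, and its Study Design text treats death as one way observation ends. If so, the error reverses: death goes to the last day of the month or 31 December and can pass the data cut-off, since there is no ceiling either. This weakens certainty about direction. It does not remove the gap.

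**Partial dates may be rare.** Protocol section 8.6 queries missing or unclear data, section 8.8 adds remote monitoring of critical variables, and section 10 asks for immediate notice of fatal SAEs. This stands: nothing in the documents shows that partial death dates are common, and the study is descriptive. With only days missing, the effect on a median is negligible.

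**Stronger readings a reader might infer, which the documents do not support:**

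- *OS and rwPFS are always shortened.* The imputed date is never later than the true one, but the unsigned interval can lengthen the computed time, as in rows 1 and 2 above.
- *Zero or negative times arise and software drops them.* As written, the interval rule cannot return less than one day. A programmer might code event minus start, and the error would then be visible, but the SAP does not say so.
- *Early AEs fall out of the tables.* Footnote 8 governs site reporting, not analysis. SAP section 8.8.1 summarises all AEs, defines no treatment-emergent filter, and defers to sponsor safety standards that are not reproduced and may contain an onset rule. Only a wrong onset day is shown, and only if those standards are silent.

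**Conclusion.** The gap is real and should be closed. On the plain reading of SAP section 7, partial death and progression dates move to the earliest possible day with no floor: on average 14.7 days early with the day missing and about 182 days early with day and month missing, if dates are uniform over the calendar. Impossible date orders follow directly. The rwPFS definition and the unsigned interval rule turn some of them into plausible but wrong times.

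The effect on summary estimates depends on a frequency the documents do not give. Under the assumed 2–20% partial dates and 24.8-month median, the median shifts by less than 0.1 month (day only) or about 0.1–1.1 months (day and month). This is mainly a matter of specification and data integrity; a large bias in the medians is not shown. For AEs, about 94% of unknown-day onsets in the first-dose month would get a date before first dose. Loss from the AE tables is not shown.

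**What to change.** In SAP section 7, name the three event types and bound them, with each bound applied within the recorded month or year:

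- **Death:** 15th of the month (day missing) or 30 June (day and month missing), but not before first dose, not before the day after the last date known alive, and not after data cut-off.
- **Progression:** not before the last assessment without progression, and not after death or data cut-off. State the starting value; the same mid-period rule would be consistent.
- **AE onset:** where the known month and year allow, not before first dose (or consent, if already exposed), unless the AE end date shows earlier onset. If the sponsor's safety standards already contain a rule, cite it instead.

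In SAP section 8, define OS and rwPFS time as event or censoring date minus start date plus one, with the sign kept, so that any remaining date-order error is visible. Report the number of imputed death, progression and AE onset dates, split by day missing and by day and month missing.

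The cost is a few lines in the SAP, a change to the date-imputation program and one summary row. No new data are needed.

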8 STATISTICAL ANALYSIS

This study has a convenience sample; thus, results may not be generalizable to the entire population with the disease. Due to the study's exploratory nature, study measures will be summarized descriptively. Furthermore, any p value reporting should be placed in a descriptive framework for hypothesis generation and any such inferential analysis is intended to guide further research.

All analyses will be conducted using SAS® version 9.4 or higher.

The intention is to analyze all available data. In the advent that COVID may cause gaps in subject data or require adjustments to statistical methodologies, our intent is to address such issues if or as needed. Both ICON and Pfizer have internal guidances and recommendations on file to assist with decision-making with regards to COVID-related data issues and these will be consulted if or as needed.

GENERAL METHODS

For continuous variables, means, standard deviations (SD), medians, minimums, maximums, and missing will be reported. For discrete variables, frequencies and percentages will be reported. Missing or unknown categories for each variable also will be presented. Percentages will be calculated excluding missing or unknown values. 95% Confidence Intervals (CI) are two-sided.

All summaries will be performed for all patients in the corresponding analysis set and by treatment combination defined at study entry within the corresponding analysis set:

- Palbociclib + Letrozole or Anastrozole
- Palbociclib + Fulvestrant
- Palbociclib + Exemestane
- Other

The baseline record is defined as the last observed measurement prior to palbociclib administration. Change from baseline is defined as the post-baseline value minus the baseline value.

Time in days between two dates will be calculated using the formula most recent date minus earlier date plus 1. For time in months, the same formula for days will be applied but then divided by 30.4. For time in years, the same formula for days will be applied but then divided by 365.25.

Variable definitions are found in Appendix 1 Data Derivation Details.

DISPOSITION OF SUBJECTS

A subject disposition summary will be reported. Subjects' study completion date and reason for premature termination will be reported in listing format. Number of subjects with initial diagnosis and with recurrent diagnosis will be reported in table and listing format.

DEMOGRAPHIC AND BASELINE CLINICAL CHARACTERISTICS

Demographic and baseline characteristics variables will be summarized for the FAS. For continuous variables (i.e., age at study enrollment, weight, height, BMI), summary statistics will be generated. For categorical variables (sex, race, ethnicity, insurance provider), the frequency and percentage of subjects in each category will be presented.

The following disease-related baseline characteristics will be summarized:

- Paloma-3 disease-free interval
- Disease free interval following treatment for early stage disease
- Treatment-free interval
- ABC/MBC diagnosis
- Duration of ABC/MBC disease
- Age of diagnosis
- Disease type
- Disease stage
- Disposition of diagnosis
- Performed biopsy and associated mutations
- Diagnostic imaging performed and imaging method
- Sites of metastases
- Estrogen Receptor (ER)/Progesterone receptor (PR) status
- Human epidermal growth factor receptor 2 (HER2) status
- Visceral status
- ECOG performance status
- Line of therapy in the ABC/MBC setting (1st line, 2nd line, 2+ line)
- Menopause status

MEDICAL HISTORY AND CONCURRENT MEDICAL CONDITIONS

Medical history and concurrent medical conditions will be summarized and presented in tabular and listing format for the FAS.

In addition, the CCI score^{17, 18} will be calculated. See Appendix 1 Data Derivation Details. Note cancer will not be included in the CCI calculation because it is the diagnosis of interest. CCI score at time of enrolment will be summarized and reported in tabular format.

MEDICATION HISTORY AND CONCOMITANT MEDICATION

Summarized information on medication history for the FAS will include:

- Prior therapy for initial diagnosis and the best response
- Prior therapy at ABC/MBC setting and the best response
 - Number of Lines of therapy
 - Therapy categories
 - Best response
- Prior chemotherapy
- Treatment free interval
- Prior radiation therapy
- Months from last prior radiation to first study dose
- Prior surgery or non-radiation procedures

All concomitant medications will be coded by therapeutic classification, subclassification, and medication using the World Health Organization Drug Dictionary (WHO Drug). A concomitant medication is defined as a medication that is ongoing as of Study Day 1, ends on or after Study Day 1, or starts on or after Study Day 1 and no more than 28 days after the last dose of study drug.

Concomitant medication of interest will be reported separately.

STUDY DRUG EXPOSURE

Overall palbociclib treatment will be summarized as below for the FAS overall and by LOT:

- Number of cycles of palbociclib received
- Length of palbociclib treatment (months)
- Treatment disposition: (still receive palbociclib, discontinued palbociclib)

Palbociclib prescribing and treatment patterns will also be explored by cycle. For each cycle, below will be summarized:

- Starting dose (if less than 125mg, present reason)
- Primary reason for selecting palbociclib for the first cycle
- Dose modification (type, dose received after modification, reason)

Treatment patterns following enrollment will be reported, which include only lines started at enrollment:

- Type of therapy received (such as chemotherapy, hormonal therapy, other therapy)
- Agent (drug) composition of the treatment regimen received
- Time from initiation of treatment to initiation of each subsequent lines of treatment

- Time from discontinuation of previous line to initiation of the subsequent line of treatment
- Time from the start to end of each treatment line (in months for the total duration). This measure will be presented overall and by the top four regimens received in the line.

The sequence of agents/combination regimens received for first-line treatment in the ABC/MBC setting and subsequent lines of treatment will be presented. The proportion of all patients with each unique sequencing pattern will be reported for the overall study sample. Type of therapy sequencing (e.g., endocrine only, chemotherapy only, endocrine therapy combined with target therapy) will also be presented in the same format.

CLINICAL OUTCOMES

rwTR, rwPFS, and OS will be assessed by LOT (1st line, \geq 2nd line) in the ABC/MBC setting for the FAS. Based on the nonrandomized, observational nature of the study design, no clinical endpoints will be separately assessed and compared between specific treatment regimens.

Real-world tumor response (complete response, partial response, stable disease, progressive disease) is determined by physician based on imaging, biopsies, biomarkers, and/or clinical judgment. Response as assessed by Response Evaluation Criteria in Solid Tumors (RECIST) criteria may not be available for all patients. rwTR will be derived as the best tumor response recorded from the palbociclib combination treatment start date until the first documentation of progressive disease. Only response assessments recorded on or before the start date of next subsequent line of treatment will be considered. The proportion of patients with a best response of complete response, partial response, stable disease, and progressive disease will be calculated and reported. Real-world response rate is defined as the proportion of patients with a best tumor response of complete response or partial response. Best tumor response, clinical benefit, and study end date are defined in Appendix 1 Data Derivation Details.

rwPFS will be estimated by LOT in the ABC/MBC setting. rwPFS is defined as time (months) from initiation of the palbociclib combination treatment to the earliest of clinician-documented progression or death due to any cause, whichever occurs first. Patients absent of the above events will be censored at the last date of response assessment without progressive disease.

OS will be estimated by LOT in the ABC/MBC setting. OS is defined as time (months) from initiation of the palbociclib combination treatment to date of death due to any cause. Patients do not have a documented death will be censored at last available visit date known to be alive.

Follow-up time will be calculated as time (months) from initiation of the palbociclib combination treatment to date of death or last available visit date. Median follow-up time and range (minimum, maximum) will be provided overall and by LOT.

Time-to-event outcomes (i.e., rwPFS, OS) will be analyzed using the Kaplan-Meier method and estimated survival curves will be displayed when appropriate. The number of patients at risk over time will be presented. A summary table will include number of patients with events, number of patients censored, and Kaplan-Meier quartiles (when estimable) accompanied by two-sided 95% confidence intervals (CIs). Based on the Kaplan-Meier life table, Survival function estimates at the specific time points (eg, 6, 12, 18, 24, 30 and 36 months) will also be reported along with two-sided 95% CIs.

Cox proportional hazards models may be developed for each time-to-event outcome when appropriate. These models would include covariates such as age, comorbidities, and hormonal partner. If performed, the validity of the proportional hazards assumption will be assessed using plots of scaled Schoenfeld residuals versus time as well as score tests for each covariate in each model. If necessary, alternative Cox modeling approaches (e.g., parametric models, restricted mean survival time, stratification, time-varying covariates) will be considered if there is evidence of nonproportional hazards. Hazard ratios for each model term, along with two-sided 95% CIs, will be computed and displayed in a table for each covariate in the final model for each outcome.

SAFETY ANALYSES

